## 7 General Considerations

### 7.1 Analysis Populations

#### 7.1.1 Full Analysis Population

All subjects who were randomised and participated in at least one post-baseline assessment

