### 5.4 Study Variables

The visit schedule is shown below:

Week	0	Phase 1										Phase 2									
		2	4	6	8	10	12	14	16	18	24	26*	28*	30*	32*	34*	36*	38*	40*	42*	48*
Active immunotherapy visit	1	2	3	4	5	6	7	8	9	10	11	-	-	-	-	-	-	-	-	-	-
Waiting list visit*	(Baseline)	-	-	-	-	-	-	-	-	-	2	3*	4*	5*	6*	7*	8*	9*	10*	11*	12*
Demographics	x																				
Other allergies	x																				
WAO score (historical)	x																				
DBPCFC (NOAEL, LOAEL, WAO score)	x									x											x
Peanut SPT	x									x											x
Other nut SPT	x									x											x
Peanut specific IgE	x									x											x
Total IgE	x									x											x
Basophil histamine release	x									x											x
Tryptase	x																				
QoL questionnaire	x									x											x
OIT updose*		x	x	x	x	x	x	x	x	x	x	x	x	x	x	x	x	x	x	x	x

*\*Only waiting list patients who are not desensitised to peanut after 24 weeks undergo immunotherapy from week 26 to 48*

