## 7.3 Missing Data

The frequency of missing data for all variables used in analysis will be summarised in a table.

To avoid using only complete case data for regression analysis when baseline covariates are missing, the ‘missing indicator’ method will be used. That is, we will include a binary indicator variable for the missingness of each covariate in regression models and we will ‘fill in’ all missing baseline covariate values with a fixed arbitrary number, say 0, to avoid software programs automatically omitting non complete cases from analysis.

[figure not shown]

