## 8 Summary of Study Data

Summaries of the study data will be presented as tables with separate columns for randomised group. All randomised patients will be included regardless of those who may not have completed the study. A table of baseline characteristics of patients will be included with a row for each covariate described in section 7.2.

Continuous variables will be summarised using means and standard deviations (or median and interquartile range if more appropriate) and categorical variables will be summarised using frequencies and percentages. The extent of missing data will be reported using annotations for the table and graphically using plots

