## **9 Efficacy Analyses**

All statistical tests described in this section use a 2-sided 5% significance level. Non-parametric tests may be used instead of parametric tests if the assumptions are not appropriate. Sensible transformations of data may be used to allow the data to fulfil assumptions.

Plots (e.g. histograms, residuals) will be used to assess the assumptions and fits of regression models.

Tests will be accompanied with a measure of effect size (e.g. difference, odds ratio etc.) and a 95% confidence interval.

All analyses will be performed on an intention to treat (ITT) basis.

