### **9.1 Primary Efficacy Analysis**

Fisher's exact test will be used to compare the incidence with desensitisation to peanut after 6 months between the intervention and waiting list group.

Multiple logistic regression will be used to adjust the odds of desensitisation for baseline characteristics described in section 7.2.

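### The SAP calls the primary analysis ITT, but its analysis set and the lack of a rule for a missing week-24 challenge make it effectively a complete-case comparison

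*SAP*

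**What the plan says.** Section 9 sets the principle: "All analyses will be performed on an intention to treat (ITT) basis". Section 9.1 gives the primary test: "Fisher's exact test will be used to compare the incidence with desensitisation to peanut after 6 months between the intervention and waiting list group".

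Section 13.1 assigns the full analysis population to Table 2.1 (that test) and to Table 2.2 (the adjusted logistic regression). Section 7.1.1 defines this population as "All subjects who were randomised and participated in at least one post-baseline assessment". The SAP does not define what counts as an assessment.

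On missing data, Section 7.3 promises a table of frequencies and then one method: "To avoid using only complete case data for regression analysis when baseline covariates are missing, the ‘missing indicator’ method will be used". It says nothing about missing outcomes. Section 4.3 defines desensitisation by what a participant can ingest without a reaction, and is silent on a participant who is not challenged.

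Section 8 says of the data summaries: "All randomised patients will be included regardless of those who may not have completed the study". Yet Table 1.1, the table of baseline characteristics, is assigned to the full analysis population.

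In the visit table of Section 5.4, the row "Active immunotherapy visit" has visits 2 to 11 after baseline in phase 1 (weeks 2, 4, 6, 8, 10, 12, 14, 16, 18 and 24). The row "Waiting list visit" has a single one, at week 24.

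**The concern.** An analyst cannot satisfy Sections 7.1.1 and 9 together once anyone is lost before week 24. Section 9 asks for all randomised participants, whereas the set named for the primary table admits only some of them. Even a participant who is in the set has no value to enter in the 2×2 table if the challenge was not done. Without a rule, that participant either drops out of Fisher's test or receives a value chosen later, possibly with the data in view.

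Participants know their arm (Section 5.3), so the reasons for missing the week-24 challenge may differ between arms. If those who leave the intervention arm are mostly treatment failures, removing them from the denominator raises that arm's success rate and the apparent effect. The SAP does not say why participants would leave, so this is an assumption, though a plausible one. What is at stake is the denominator of the primary endpoint and the label put on the result.

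**Working it through.** **1. The plan's own sample size.** Inputs from Section 6: 64% v 30%, Fisher's exact test, two-sided 5%, 90% power, 5% drop-out. Exact enumeration gives power 0.896 at 48 per arm and 0.906 at 49, so 49 is right. Inflation: 49/(1 − 0.05) = 51.6, rounded up to 52 per arm, 104 in all. The sample size is not at fault. Adding participants to replace drop-outs does suggest that drop-outs were expected to contribute no outcome, which fits a complete-case analysis.

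**2. Who is in the primary table, under each reading of assessment.**

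| Reading | Intervention participant who stops after week 2 and is not challenged | Waiting-list participant who misses week 24 | Participants in Fisher's test |
|---|---|---|---|
| Updose visits count | in the set, no outcome | out of the set | those challenged, unless an unstated rule supplies a value |
| Only outcome measurements count | out of the set | out of the set | those challenged, unless an unstated rule supplies a value |

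Under the first reading the set treats the arms differently. Under the second it is nominally the same for both. Neither is ITT, and if participants without a challenge simply drop out of the test, both readings give the same 2×2 table.

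**3. Size of the shift.** Illustrative counts close to the planning rates: 33/52 (63.5%) v 16/52 (30.8%) among all randomised. Assumption: every missing participant is a failure. The SAP gives no drop-out rates by arm, so the numbers missing are assumed over a range; 5% of 52 is 2.6, about 3 per arm.

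| Left out (intervention, waiting list) | Rates compared | Difference (points) | Odds ratio |
|---|---|---|---|
| none: missing counted as failures | 33/52 v 16/52 | 32.7 | 3.91 |
| 3, 3 | 33/49 v 16/49 | 34.7 | 4.25 |
| 3, 0 | 33/49 v 16/52 | 36.6 | 4.64 |
| 8, 0 | 33/44 v 16/52 | 44.2 | 6.75 |
| 0, 3 | 33/52 v 16/49 | 30.8 | 3.58 |

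The last row shows that the bias can also go the other way.

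**4. False-positive rate.** Suppose the true success rate is 30% of all randomised in both arms, and m intervention failures are left out. The intervention rate among those analysed is then 0.30 × 52/(52 − m). The exact two-sided rejection rate of Fisher's test is 0.029 for m = 0, 0.041 for m = 3, 0.050 for m = 5, 0.073 for m = 8 and 0.095 for m = 10. It passes the nominal 5% only with one-sided losses well above the planned 3.

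**5. Power if missing is counted as failure.** Here 64% and 30% are taken as the rates among those challenged, with 52 per arm.

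- 5% missing in both arms: 0.64 × 0.95 = 60.8% v 0.30 × 0.95 = 28.5%; exact power 90.4%.
- 5% missing in the intervention arm only: 60.8% v 30%; 87.3%.
- 10% missing in both arms: 57.6% v 27%; 87.0%.

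**The case against.** The strongest reply is that little changes at the drop-out the SAP expects. With 3 missing per arm the difference moves by 2 points, and the rejection rate stays below 5% even if 3 failures are lost from the intervention arm alone. Missing data would also be visible, since Section 7.3 tabulates them, Section 8 annotates and plots them, and Section 8.1 adds a CONSORT diagram. This stands, and it limits the severity. It does not settle which denominator the primary test uses.

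A reader might infer that the population rule demonstrably keeps intervention drop-outs and removes waiting-list drop-outs. The SAP does not establish that. The only intervention-arm activity scheduled before the outcome measurements is updosing, which is treatment, and Section 5.1 speaks of assessing all participants after six months. If assessment means outcome measurement, the rule is the same in both arms. Even on the other reading, the asymmetry reaches the primary test only through a rule that gives unchallenged participants an outcome, and the SAP has none.

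The sentence in Section 8 is also weaker evidence than it looks. It governs descriptive summaries and so conflicts with the population given for Table 1.1, not with the primary test.

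Finally, counting missing as failure is not neutral. Control participants are expected to succeed 30% of the time, so scoring missing waiting-list participants as failures can favour the intervention. With 30% true success in both arms and only waiting-list outcomes missing, the rejection rate is 0.052 with 8 missing and 0.066 with 10. This also stands, and is why a worst-case analysis belongs with the fix.

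**Conclusion.** The point holds as a conflict between a stated principle and the rules meant to deliver it. Section 9 promises ITT; the population in Section 7.1.1, used in Table 2.1, together with the absence of a missing-outcome rule, yields an effectively complete-case primary analysis. This is true on either reading of assessment. Different treatment of the arms is a conditional addition, which arises only if updose visits count.

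The size depends on drop-out that the SAP does not give by arm, and on the assumption that missing participants are failures. At about 3 per arm the shift is 2 points. It becomes material when losses are larger or one-sided: 11.5 points (44.2 − 32.7) with 8 intervention failures left out, and a false-positive rate of 0.073 in the matching null case.

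It would be too strong to say that the result will be biased towards the intervention, since the direction depends on who is missing. It would also be too strong to say that the fix costs no power: the 90% target is kept with equal 5% drop-out, but not in the other cases shown. Severity: should be fixed.

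**What to change.** - In Section 7.1.1 and Section 13.1, define the set for the primary analysis as all randomised participants, in the arm to which they were allocated. This also brings Table 1.1 into line with Section 8.
- In Section 7.3, state that a missing week-24 challenge counts as not desensitised in both arms for the primary endpoint, and likewise as no response for the 800 mg endpoint.
- Add two sensitivity analyses: complete cases, and a worst case in which missing counts as success in the waiting-list arm only. In the illustration with 3 missing per arm, the worst case would be 33/52 v 19/52, a difference of 26.9 points.
- If a set based on assessments after baseline is kept for other purposes, define assessment.

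The cost is SAP wording and two extra rows of results. Reported success rates may be slightly lower. Exact power with 52 per arm is 90.4% if 5% are missing in both arms, and about 87% if only the intervention arm loses 5%.

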### 7.1.2 Per-Protocol Population

The criteria for per-protocol analysis of the outcome of peanut challenge at the end of immunotherapy will consist of: desensitisation and continuation of immunotherapy up to the maintenance dose of 800mg protein.

### 7.1.3 Safety Population

All subjects who received any study treatment (including control) and are confirmed as providing complete follow-up regarding adverse event information.

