## 6 Sample Size

Based on Fisher's exact test with 90% power and 5% significance (two-sided) a sample size of 49 in each group is sufficient to detect proportions of participants with desensitisation to peanut of 64% and 30% in the intervention and control group respectively. Allowing for 5% drop out increases the sample size to 52 participants in each group and 104 subjects overall.

Based on the above we would expect 35 waiting list group patients to proceed to the active intervention in phase 2. To confirm efficacy of immunotherapy the success rate of all participants (intervention and phase 2 waiting list) should be within 10% of the success rate seen in intervention participants alone in phase 1.

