### 10.2 Adverse Events

A table summarising the incidence of the following adverse events per peanut dose will be produced: mouth itching, abdominal pain, nausea, vomiting, diarrhoea, urticaria, angioedema, erythema, rhinitis, wheezing, laryngeal oedema, cardiovascular collapse, fainting, admission to intensive care unit (ITU), serious

adverse reaction, suspected unexpected serious adverse event (SUSAR), use of nebulised beta 2 agonist and use of intramuscular adrenaline.

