### 10.3 Deaths, Serious Adverse Events and other Significant Adverse Events

The summary statistics will be produced in accordance with section 8.

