Comparison of change in peanut immunological outcomes between treatment groups	2.6	Full analysis	Peanut IgE Total IgE Peanut SPT Other nut SPT Basophil histamine release CD63MFI (AUC) Basophil histamine release %CD63 positive cells (AUC)	Baseline and 6 months	Treatment	median, range, difference, 95% CI	Mann-Whitney U tests
Comparison of change in WAO score between treatment groups	2.7	Full analysis	WAO score	Baseline and 6 months	Treatment	median, range, difference, 95% CI	Mann-Whitney U tests
Predictors of treatment response	2.8	All patients who underwent immunotherapy	Response to immunotherapy	6 months (or 12 months for Waiting list group)	Treatment Age Sex Asthma Eczema Rhinitis Weight	odds ratios, 95% CI	Logistic regression

Sensitisation to tree nuts

Peanut specific IgE

Peanut SPT wheal diameter

Basophil AUC of CD63MFI against peanut protein concentration

QoL score

Family history of allergy peanut

Baseline NOAEL

Adverse events per dose	2.9	Safety population	Mouth itching Abdominal pain Nausea Vomiting Diarrhoea Urticaria Angioedema Erythema Rhinitis Wheezing Laryngeal oedema Cardiovascular collapse Fainting Admission to ITU Serious adverse reaction SUSAR	End of study	Treatment	n, %	NA
-------------------------	-----	-------------------	---	--------------	-----------	------	----

Use of nebulised beta 2 agonist

Use of intramuscular adrenaline

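### The safety population requires complete adverse-event follow-up, so Table 2.9 drops recorded reactions of treated participants who are later lost, and this conflicts with SAP section 8

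*SAP*

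**What the plan says.** SAP section 7.1.3 defines the safety population by two conditions. The first is receipt of treatment: "All subjects who received any study treatment (including control". The second follows directly: "and are confirmed as providing complete follow-up regarding adverse event information". Neither 'confirmed' nor 'complete' is defined.

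Section 10.2 describes the adverse-event analysis: "A table summarising the incidence of the following adverse events per peanut dose will be produced". In section 13.1 this becomes Table 2.9, with the population given as "Safety population", the time point as end of study, and no formal test. Its rows run from mild symptoms to laryngeal oedema, cardiovascular collapse, ITU admission, serious adverse reactions, SUSARs and intramuscular adrenaline. Section 13.1 lists no other adverse-event table.

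Section 8 sets a different rule for summaries of study data: "All randomised patients will be included regardless of those who may not have completed the study". Section 10.3, on deaths and serious or significant events, refers back to it: "The summary statistics will be produced in accordance with section 8". Section 10.1, on exposure, does the same.

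The only technique in section 7.3 for handling missing values is confined to regression covariates: "To avoid using only complete case data for regression analysis when baseline covariates are missing". It has no rule for partly observed adverse-event data, and no supporting analysis on all treated subjects is planned.

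**The concern.** Whether follow-up was complete is known only after treatment, and it may depend on the reactions that the table is meant to measure. Once a participant fails the condition, everything they contributed goes, including reactions recorded while they were still under observation. Those data are valid; what is missing is only the time after last contact.

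If children who react badly are more often lost, the reported incidence is too low for the treatment whose safety is in question. Because 'complete' is undefined, membership would also be decided after events are known, in a trial where section 5.3 says participants know their group.

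The second problem is consistency. A serious reaction in a child later lost to follow-up would be kept under section 10.3 but be absent from Table 2.9, which has its own rows for serious adverse reactions and SUSARs.

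**Working it through.** **1. The plan's own figures.** Section 6 gives 49 per group for 64% against 30%, with Fisher's exact test, 90% power and two-sided 5%. This reproduces: exact power is 0.906 at 49 per group and 0.896 at 48. The dropout step, "Allowing for 5% drop out increases the sample size to 52 participants in each group", also reproduces: 49/0.95 = 51.6, rounded up to 52. The point does not depend on the sample size. The margin 52 − 49 = 3 is used below only as a convenient number of lost children. The 5% allowance was made for the desensitisation comparison and does not estimate lost adverse-event follow-up.

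**2. What the exclusion does to a per-dose rate.** Let E be events and D doses, with subscript f for followed and l for lost participants.

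- As written: r_f = E_f / D_f
- All treated: R = (E_f + E_l) / (D_f + D_l)
- Difference: r_f − R = [D_l / (D_f + D_l)] × (r_f − r_l), where r_l = E_l / D_l

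Exclusion removes both events and doses. The table understates incidence only if r_l exceeds r_f, is unbiased if they are equal, and overstates if r_l is lower.

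**3. Illustration with assumed counts.** The SAP gives no event rates, dose counts or loss rates for adverse-event follow-up. Assume 49 followed children with 150 doses each and 3 adrenaline uses, and 3 lost children with 30 doses each.

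- D_f = 49 × 150 = 7,350; D_l = 3 × 30 = 90; total 7,440
- As written: 3/7,350 = 0.041% per dose, whatever happened to the lost children

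| Adrenaline uses among the lost | All treated | As written relative to all treated |
|---|---|---|
| 0 | 3/7,440 = 0.040% | about 1% higher |
| Same per-dose risk (90 × 3/7,350 = 0.04 expected) | 0.041% | equal |
| 1 | 4/7,440 = 0.054% | about 24% lower |
| 2 | 5/7,440 = 0.067% | about 39% lower |

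The last row assumes 2/90 = 2.2% per dose among the lost, about 54 times the rate in the rest. It shows how few events are needed to move the table; it is not a forecast.

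**4. The same question per child, also assumed.** Take 52 treated, 3 excluded, and an event in 10% of the 49 followed. The table shows 10.0%. The all-treated figure is (0.10 × 49 + 3q)/52, where q is the proportion of the excluded with the event:

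- q = 0.10: 5.2/52 = 10.0%
- q = 0.5: 6.4/52 = 12.3%
- q = 1: 7.9/52 = 15.2%

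**5. Who is treated by end of study.** Section 6 expects 35 waiting-list participants to go on to immunotherapy, so about 52 + 35 = 87 participants would contribute doses, not 52.

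**6. The sections side by side.** Consider a child who is dosed, has a serious reaction and is then lost. Under sections 8 and 10.3 the child is randomised, so the event is summarised. Under section 7.1.3 and Table 2.9 follow-up is incomplete, so the child, the event and the doses are out. The SAP does not say which count governs.

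**The case against.** The strongest reply is that the harm is limited. Sections 10.1 and 10.3 follow section 8 and so appear to keep every randomised patient for exposure, deaths and serious events. Table 2.9 is descriptive, and no efficacy result depends on it. A child who stops immunotherapy but is fully followed for adverse events stays in the safety population. Because Table 2.9 is per dose, the denominator falls along with the numerator.

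All of this is correct, and it rules out two stronger readings. A reader might infer that the clause removes the children who stopped because of reactions and so definitely biases the rates downward. The SAP does not support that: the clause acts on lost follow-up rather than stopped treatment, and the link between loss and reactions is a reasonable inference, not something the document states. A reader might also infer that rare serious events could disappear from the report. They could disappear from Table 2.9, but on the section 8 reading they would remain under section 10.3.

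The reply does not remove the defect. The section 10.3 route leaves two possible counts of the same kind of event, unreconciled. Table 2.9 items that are not serious or significant events have no such second route. The per-dose basis protects against bias only when the excluded have the same per-dose risk, and the plan offers no way to check that.

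**Conclusion.** The point holds in a limited form. As written, section 7.1.3 makes safety-population membership depend on a condition met after treatment, and Table 2.9 then discards events and doses already observed in anyone who fails it. This may bias per-dose incidence downward. The size is unknown, and there is no bias if the excluded have the same per-dose risk. The contrast of 0.067% with 0.041% rests wholly on assumed counts and on strong enrichment of events among the lost. The conflict between section 7.1.3 with Table 2.9 and sections 8 and 10.3 needs no such assumption; it follows from the text. Sample size and efficacy analyses are unaffected.

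**What to change.** - In section 7.1.3, delete the complete-follow-up condition. Define the safety population as all subjects who received any study treatment, including control, and count all events and doses up to last contact.
- State that waiting-list participants contribute their phase 2 immunotherapy doses and events as treated.
- Report beside Table 2.9 the number with incomplete adverse-event follow-up, by group.
- Align section 7.1.3 and Table 2.9 with sections 8 and 10.3, so that serious events are counted on one stated basis.
- If wanted, keep an analysis of those with complete follow-up as supplementary.

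The cost is a short SAP edit and one added reporting line. No sample-size figure or efficacy analysis changes. Reported adverse-event rates may be slightly higher, and some participants will contribute only partial follow-up, which the added line makes visible.
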